Study Protocol Cover page

Title: Effectiveness, safety, and tolerability of different estradiol dosing regimens in transgender females.

NCT Number: NCT05010707

Date: May 26, 2022

Washington University in St. Louis

Version Date: May 26th, 2022

Principal Investigator: [name]

Study Title: Effectiveness, safety, and tolerability of different estradiol dosing regimens in transgender females.

Faculty Sponsor: [name]

- **Objectives**

The purpose of this open label, pilot, randomized clinical trial is to evaluate the effectiveness, safety and tolerability of estrogen use in transgender female and the degree of testosterone suppression achieved in this population when placed on sublingual 17-beta estradiol in comparison to transdermal 17-beta estradiol for gender affirming pharmacological therapy over the first two-years of treatment.

This study is important because, to our knowledge, this is the first randomized clinical trial evaluating the effectiveness, safety, and tolerability of estrogen in transgender female. There are no previous data comparing the different presentation of estrogen options in transgender women; therefore, this clinical trial will determine the best strategies and methods required to develop a larger randomized clinical trial. This study will also provide information useful to close the medical knowledge gap to provide safe and competent care to transgender female patients.

Aims

Aim 1. In this randomized clinical trial, we will evaluate the degree of testosterone suppression by measuring total testosterone level in transgender female patients undergoing hormonal affirming therapy randomized to sublingual 17 beta estradiol or transdermal 17 beta estradiol, in conjunction with spironolactone (antiandrogen), for a period of 2 years.

Hypothesis 1a. Transgender females undergoing hormonal affirming therapy randomized to sublingual estradiol with multiple daily doses will have higher degree of testosterone suppression. This hypothesis is based on the rationale that higher peak levels obtained with sublingual estradiol will suppress the hypothalamic-pituitary axis to a greater degree than the more stable levels achieved with transdermal delivery. Multiple studies (15) (18) in cisgender women describe the daily biological rhythm of estradiol, and a diurnal cycle of estradiol exhibiting an early morning peak followed by two to four recurrent cycles. However, there is no information on transgender patients regarding best pharmacological intervention (continuous vs pulsatile) to suppress the hypothalamic-pituitary-gonadal axis.

Aim 2. In this randomized clinical trial, we will determine the impact on liver enzymes, metabolic profile, and thrombogenic factors in transgender female patients undergoing hormonal affirming therapy randomized to sublingual 17 beta estradiol or transdermal 17 beta estradiol, in conjunction with spironolactone (an antiandrogen), for a period of 2 years.

Hypothesis 2a. Transgender female patients on sublingual estradiol will have higher levels of estrone, which will lead to an increase on thrombogenic factors and changes in metabolic factors. It has been determined that higher estrone levels in cisgender females, has been linked with a high incidence of venous thromboembolism, breast cancer, and endothelial inflammation. An explanation for the higher thrombotic risk in postmenopausal women includes high production of thrombin due to high levels of estrone (12). Hypothesis 2b. Higher fat mass after FHT will have a negative impact on insulin sensitivity. Estradiol therapy in transgender women appears to be associated with an increase in fat mass and decrease in lean mass, although prospectively controlled data is limited (11). The increase in body fat associated with estrogen therapy raises questions about the effect on insulin sensitivity and cardiovascular risk.

Purpose, Background, and Rationale

- **Background and Significance**

Transgender individuals experience discordance between their self-identified gender and biological birth sex (1). Some transgender individuals experience gender dysphoria which the Diagnostic and Statistical Manual of Mental Disorders (DSM-5) defines as clinically significant distress or impairment in social, occupational, or

other key areas of functioning. Increasing numbers of adolescents seek care at gender identity centers in Western Countries (3).

Studies using short self-reports of gender identity and its variants suggest that 0.17%-1.3% of adolescents and young adults identify as transgender (4). Even using the conservative estimate of 0.3%, the number of people living in the United States who identify as transgender is nearly 1 million. Health care for this population has historically been, and continues to be, overlooked by governmental, health care, and academic establishments (16). This has led to a wide range of health disparities and poor health outcomes compared with their cisgender counterparts (17). Given the widespread acknowledgment of the health care needs of transgender people, priority should be given to those actions that will ensure timely access to appropriate care. Such action includes, first and foremost, coverage of transition care and a requirement to ensure safe, appropriate, and sensitive care in health centers (16) (17).

Transgender women seek feminizing hormone therapy (FHT) to reach feminine physical features consistent with their gender identity. The goal of FHT is to achieve feminine features and maintain estradiol levels within the normal female range while suppressing endogenous testosterone (5). Both the World Professional Association for Transgender Health (WPATH) and the Endocrine Society have created transgender-specific guidelines that serve as a framework for providers caring for gender minority patients. These guidelines are mostly based on clinical experience from experts in the field. Guidelines for estrogen therapy in transgender women are loosely based on treatments used for postmenopausal women (6). Therefore, stronger evidence is needed to guide clinicians on best clinical practices for this population.

The current approach to FHT is not uniform or FDA approved and depends on the health care system, cost considerations, and differences in the regional availability of estrogens and antiandrogens. A typical regimen includes estrogen to provide feminizing effects in conjunction with therapy to block testosterone (antiandrogens or gonadotropin-releasing hormone [GnRH] analogs). Estrogen also inhibits testosterone secretion (9)(13). Ethinyl estradiol was previously the mainstay of most estrogen-directed therapies; this is no longer the case due to its increased risk of cardiovascular death and increased incidence of deep venous thrombosis (7). 17-beta estradiol, which can be provided in tablet, patch, and injection, is currently the preferred formulation (8).

Androgen blockade is usually established in all transgender females undergoing feminizing therapy and is achieved by either using gonadotropin blockade or antiandrogens. The latter, defined as medications other than estradiol which are used to decrease the synthesis of or actions of androgens. In the United States, spironolactone is commonly prescribed. Cyproterone acetate (CPA) is not licensed for use in the United States; however, CPA appears to be favored in many European countries and forms standard care as part of the European Network for the Investigation of Gender Incongruence (ENIGI) treatment protocol (10).

- **Innovation**

Transgender female patients suffer from poor health outcomes compared with their cisgender peers, mostly because feminizing therapy with estrogen has been based on data from postmenopausal women and expert opinion. This represents a critical gap in knowledge that prevents the delivery of safe and appropriate care for the transgender population. This proposal is innovative because the project is aimed to study the tolerability, safety, and differences in testosterone suppression of the most common 17-beta estradiol presentation while using the same antiandrogen (spironolactone). Any differences detected between the groups will be attributed to the estrogen effect based on their route of administration. Moreover, this randomized clinical trial will allow the collection of valuable preliminary data to determine the best strategies and methods required to develop a larger randomized clinical trial. This knowledge will set the stage for future feasible and sustainable interventions for transgender youth to improve health related outcomes.

- **Methods, Research Plan, and Design**

- **Study design**

This study will be a prospective 2-year randomized, open label, clinical trial, using daily dose sublingual versus twice daily dose sublingual versus transdermal 17-beta estradiol in transgender female patients. Primary outcome is degree of testosterone suppression. Secondary outcome to measure safety and tolerability will

include liver enzymes, thrombogenic, and metabolic factors. Patients will be evaluated every 6 months during the length of the study

b. Subjects

Inclusion criteria: Female transgender patients between the ages of 18 to 45 years of age who are seen at the Washington University Transgender Center. Patients must have met the eligibility and readiness criteria for gender-affirming hormone therapy.

Exclusion criteria: Use of GnRH agonist for the last 12 months, history of liver disease, dyslipidemia requiring treatment, drug use, alcohol use (>2drinks per day), cigarette smoking, history of blood clot (venous thromboembolism, pulmonary embolism), history of hyperkalemia, history of Addison's disease, concomitant use of eplerenone.

Patients who have been referred to the Washington University Transgender Center for feminizing hormonal therapy and meet the inclusion criteria, will undergo consent process before initial evaluation. Methods for recruitment includes phone calls, emails, letters, and EPIC slicer dicer. For consent, physical or electronic consent form will be provided.

If consent is obtained, patients will be assigned to either daily sublingual vs twice daily sublingual vs transdermal 17-beta estradiol. Assignment will be done through block randomization.. Using the inclusion criteria, our center provides care to 150-200 new transgender female patients in a year for initiation of female hormone therapy.

We aim to enroll a total of 70 patients. This is a pilot study, which results will guide the feasibility, design, and implementation of a larger clinical trial. To account for 15% of potential dropout, we have planned to enroll a total of 80 patients.

- Research Plan**

The proposed clinical trial involves 2 research aims to be conducted over two years (Table 1). Subjects will be recruited from the Washington University Transgender Center. The Center is projected to see more than 1,000 patients every year, of which 150-200 are new transgender female patients for initiation of FHT.

Patients who agree to participate in the study and meet inclusion criteria will undergo the evaluation described in Table 2. Data of interest will be collected on all patients enrolled and will be saved on a database created in Research Electronic Data Capture (REDCap). Information to be collected will include:

1. Demographic and anthropometric variables: Parameters will be routinely collected through chart review.
2. Laboratory testing: During each visit, we will obtain hormone levels, coagulation factors, metabolic factors, electrolytes level. A hematologist will review the lab results and communicate any recommended interventions (including stopping medication) to the participant's treatment team.

Initial evaluation will include patient history, physical examination, and baseline labs. During the initial visit, patients will be started on spironolactone and 17-beta estradiol transdermal or or daily sublingual or twice daily sublingual based on their treatment group assignment. Our team will check hormonal levels every 4 weeks (+/- 2 weeks) until estradiol level is within goal (see dosing guidelines) as established by standard of care. Once patients are started on estradiol, they will be asked to attend 6 more visits for the 2 years duration of the study as described in table 2.

Dosing guidelines:

Per the current standard of treatment, all study medications are initiated at the lowest available clinical dose and titrated to effectiveness at the study clinician's discretion by 6 months of study participation, using plasma total testosterone level in the cisgender female range (<50ng/dL) with serum estradiol level that should not excess the peak physiologic range 100-200 pg/mL. In some cases, medication doses will be titrated at monthly study follow up visits to optimize treatment response.

Spironolactone:

Starting dose will be 50 mg daily

Plan to increase 50 mg monthly to standard dose of 200 mg daily

For patients randomized to transdermal (patch) estradiol:

Starting dose will be 100 mcg/24hrs

Plan to increase by 100 mcg/24hrs every month

Max dose 400 mcg/24hrs

Goal is to achieve a serum estradiol level between 100-200 pg/mL and to suppress testosterone to cisgender female levels

Estradiol levels will be measured in the morning (fasting sample)

For patients randomized to daily sublingual estradiol:

Starting dose will be 2 mg daily

Plan to increase every month by 2 mg daily

Goal is to achieve serum estradiol level between 100-200 pg/mL and to suppress testosterone to cisgender female levels.

Estradiol levels will be measured in the morning (fasting sample).

For patients randomized to twice daily dose sublingual estradiol

Starting dose will be 1 mg twice daily

Plan to increase every month by 2 mg daily

Goal is to achieve serum estradiol level between 100-200 pg/mL and to suppress testosterone to cisgender female levels

Estradiol levels will be measured in the morning (fasting sample).

Table 1. Planned Research Timeline

Data cleaning and analysis										•	•	•	•
Grant application				•	•	•	•						
Final results manuscript										•	•	•	
Presentation preparation										•	•	•	

Table 2. Description of the evaluation and laboratory testing in each visit during the clinical trial

Study visit	Baseline	6 months +/- 2 months	12 months +/- 2 months	18 months +/- 2 months	24 months +/- 2 months
Anthropometric measurement	•	•	•	•	•
Metabolic factors	•	•	•	•	•
Hormone levels	•	•	•	•	•
Electrolytes	•	•	•	•	•
Liver function test	•	•	•	•	•
Coagulation factors	•	•	•	•	•
Lipid Panel	•		•		•

- Benefit/Risk assessment**

i. Benefits

Direct benefits from this study to participants are anticipated. During the research study, their tolerability and side effects will be monitored closely so any changes can be detected earlier. Also, participants may feel gratified by contributing to the field. Patients will have the opportunity to help us improve services and treatment options for them and future generations.

ii. Risks

Potential risks with this study are no different than the risks that may occur while receiving gender affirming therapy. This may include changes in their lipoprotein profile and triglycerides level (14) and increase risk of venous thromboembolism, diabetes, high blood pressure, coronary heart disease, hepatotoxicity. While the patient is receiving gender affirming therapy, the investigators will provide careful attention to laboratory results.

Laboratory testing will be obtained every 3 months for the first year, and every 6 months on the second year. For this purpose, placement of an intravenous (IV) access may be required. IV access or venipuncture may be associated with possible minor discomfort or pain when inserted.

- Statistical methods and Data Analysis**

Baseline characteristics and laboratory results will be reported as mean \pm SD, median (interquartile range), or percentages. Independent T-test will be used to analyze the difference between treatment groups. We may use Wilcoxon rank sum test in case of non-normal distribution.

g. Limitations and contingent plans

A potential limitation to this study is the difficulty of recruitment since the PI is a First Year Clinical Fellow with a heavy clinical rotation. Our project is also supported by the director of the Washington University Transgender Center which will improve the recruitment of patients. Also, the co-directors of the Washington University Transgender Center at St Louis Children's Hospital are supporting the project, therefore, we could increase our enrollment numbers by recruitment patients seen in their clinic. Another limitation is the cost of the entire panel of thrombogenic factors. We could address this by just testing the most valuable test (thrombin) which has been used in previous research to assess the thrombotic risk in postmenopausal women on hormone replacement therapy.

- **References**

- Unger CA. Hormone therapy for transgender patients. *Transl Androl Urol.* 2016;5(6):877-884. doi:10.21037/tau.2016.09.04
- American Psychiatric Association. Diagnostic and Statistical Manual of Mental Disorders. 5th ed. Washington, DC: American Psychiatric Press; 2013
- Unger CA. Hormone therapy for transgender patients. *Transl Androl Urol.* 2016;5(6):877-884. doi:10.21037/tau.2016.09.04
- Unger CA. Hormone therapy for transgender patients. *Transl Androl Urol.* 2016;5(6):877-884. doi:10.21037/tau.2016.09.04

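### Aim 2 has an uncontrolled false-positive risk: no thrombogenic or metabolic analyte, visit or multiplicity rule is fixed, yet any difference is to be credited to estrogen route

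*Combined protocol and SAP*

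**What the plan says.** The Aims section sets Aim 2 broadly: "we will determine the impact on liver enzymes, metabolic profile, and thrombogenic factors". Hypothesis 2a expects higher estrone on sublingual estradiol, "which will lead to an increase on thrombogenic factors and changes in metabolic factors". Estrone is named and given a direction. Thrombogenic factors have a direction but no named factor. Metabolic factors have neither.

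The Study design section describes three arms, "using daily dose sublingual versus twice daily dose sublingual versus transdermal 17-beta estradiol", and makes liver, thrombogenic and metabolic measures the secondary safety and tolerability outcomes. Table 2 schedules metabolic factors, coagulation factors and liver tests at 6, 12, 18 and 24 months after baseline, and the lipid panel at 12 and 24 months.

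The inferential plan in Statistical methods and Data Analysis is "Independent T-test will be used to analyze the difference between treatment groups", with a Wilcoxon rank sum test as the alternative for non-normal data. No significance level, contrast, visit or multiplicity rule is given.

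The Innovation section adds: "Any differences detected between the groups will be attributed to the estrogen effect based on their route of administration". The Limitations section mentions a single thrombogenic measure, but only as a response to cost: "We could address this by just testing the most valuable test (thrombin) which has been used in previous research".

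**The concern.** Two whole families of laboratory values are compared over several visits, and nothing says in advance which comparison carries the conclusion. For metabolic factors, either a rise or a fall in any value would fit the prediction. If each value is tested at each visit without adjustment, some differences will reach p<0.05 by chance, and the Innovation wording leaves no room to call them chance. The gap remains even if the arm contrast is fixed as sublingual versus transdermal, which is how Aim 2 is worded.

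At stake is what the trial can say about the thrombogenic and metabolic safety of the regimens. The study is meant to shape a larger trial, and a chance signal against one regimen could be carried into that design as an estrogen effect.

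**Working it through.** The plan states no error rate for Aim 2, so there is no figure of its own to reproduce.

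**Inputs from the documents.** Target of 70 patients (Subjects); three arms (Study design); four post-baseline visits, with lipids at two of them (Table 2); two-sample tests (Statistical methods).

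**Assumptions, because the documents are silent.**
- Two-sided 0.05 per test and no true difference.
- Arms of 23, 23 and 24, so 46 sublingual versus 24 transdermal.
- Correlation between a patient's visits 0.5–0.7, and between analytes 0–0.3.
- Three illustrative panels (thrombogenic + metabolic + lipid): 1+1+1, 3+3+4 and 5+5+4. Liver enzymes are not counted.

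**Step 1: number of tests for one contrast at all visits.** (thrombogenic + metabolic) × 4 + lipid × 2:
- 1+1+1: 2 × 4 + 1 × 2 = 10
- 3+3+4: 6 × 4 + 4 × 2 = 32
- 5+5+4: 10 × 4 + 4 × 2 = 48

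**Step 2: chance of at least one p<0.05 if tests were independent.** 1 − 0.95^m gives 14% for m = 3, 40% for m = 10, 51% for m = 14, 81% for m = 32 and 91% for m = 48. Correlation lowers these, so a simulation is needed.

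**Step 3: simulation under no effect.** Normal laboratory values, pooled-variance t-tests, at least 1,500 simulated trials per setting. The standard error is at most √(0.25/1500) = 1.3 percentage points.

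| Panel | One visit, any difference | All visits, any difference | All visits, thrombogenic increase AND metabolic or lipid change |
|---|---|---|---|
| 1+1+1 | 13–14% | 30–35% | 1–3% |
| 3+3+4 | 35–40% | 65–75% | 9–12% |
| 5+5+4 | 45–52% | 77–87% | 15–24% |

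One test named in advance gives 5%. If all three arm pairs were tested at all visits, the any-difference figures would be about 58–68%, 91–97% and 96–99%. Aim 2 as worded does not call for that.

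**Step 4: the visit count is itself unsettled.** Study design says "Patients will be evaluated every 6 months during the length of the study"; the Risks section says "Laboratory testing will be obtained every 3 months for the first year, and every 6 months on the second year". The first gives four post-baseline laboratory times and the second six (3, 6, 9, 12, 18 and 24 months). These passages must be reconciled. With six times and lipids still at two, the smallest panel gives 2 × 6 + 2 = 14 tests instead of 10.

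**The case against.** The strongest reply is that the any-difference rule is not in the documents. The plan gives no significance level and does not say that every analyte will be tested at every visit. The Innovation sentence follows a remark that all arms share the same antiandrogen. In context it argues that the comparison isolates route; it is not a criterion for declaring an effect, and it does not itself raise the error rate. Hypothesis 2a is also narrower than an any-difference rule: it names estrone with a direction, predicts a thrombogenic increase, and joins that to metabolic change. Read as requiring both, the chance falls to the last column of the table, and requiring higher estrone as well could only lower it. Finally, these are secondary outcomes in a pilot, where unadjusted safety laboratory results are common and missing a signal also has a cost.

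Most of this stands, and it limits the claim. A reader might infer that Aim 2 is likely to report a treatment effect even when the regimens do not differ. The documents do not support that: the analyte count, visits, significance level and decision rule are all unstated, and the smallest panel stays well below 50% with the sublingual versus transdermal contrast.

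The reply does not remove the gap. Nothing in the plan commits to the narrower reading, nothing labels Aim 2 exploratory, and the attribution sentence as written admits no chance finding. One analyte per family is also a low count, since the protocol speaks of a lipid panel and of an entire panel of thrombogenic factors.

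**Conclusion.** The concern holds as an uncontrolled false-positive risk of unknown size. Its source is mainly the statistical section, which sets no significance level, contrast, visit or multiplicity rule; the open wording of Hypothesis 2a and the attribution sentence compound it. On every any-difference reading examined with more than one test, the chance of a false positive exceeds 5%, from 13–14% for the smallest panel at one visit to 77–87% for the largest at all visits. On the joint reading it can fall below 5%. These figures rest on the assumed panels, correlations and two-sided 0.05 level.

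A reader might also infer that thrombin must be the sole deciding test. The protocol mentions it only as a cost fallback, singles out no visit for it, and would lose the estrone and metabolic parts of Hypothesis 2a if it alone decided. For secondary outcomes in a pilot, this is a cheap and worthwhile improvement, not a fatal flaw.

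**What to change.** 1. In Statistical methods and Data Analysis, state that thrombogenic, metabolic, lipid and liver results are exploratory. Report them as sublingual-versus-transdermal differences with 95% confidence intervals, or with Benjamini-Hochberg p-values across the family.
2. In Innovation, replace the sentence crediting every detected difference to estrogen route with wording that treats isolated Aim 2 differences as signals for the larger trial.
3. Optionally, name one lead thrombogenic measure and visit in advance. The choice is the sponsor's.

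The cost is protocol wording only: no new samples, visits or patients. The downside is that an isolated p<0.05 can be reported as a signal but not as a confirmed effect. Showing every estimate with its interval keeps possible safety signals visible.

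### Hypothesis 2b has no planned analysis that can answer it, and the estrone link within Hypothesis 2a is untested, because the only planned tests compare treatment arms

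*Combined protocol and SAP*

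**What the plan says.** Aim 2 is framed by randomized route and concerns liver enzymes, metabolic profile and thrombogenic factors. Two hypotheses sit under it.

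- **2a:** patients on sublingual estradiol "will have higher levels of estrone, which will lead to an increase on thrombogenic factors and changes in metabolic factors". This contains an arm contrast (sublingual against transdermal) and a stated link from estrone to the other factors.
- **2b:** "Higher fat mass after FHT will have a negative impact on insulin sensitivity". No arm is named.

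The section Statistical methods and Data Analysis is three sentences long. It gives descriptive summaries, then "Independent T-test will be used to analyze the difference between treatment groups", then "We may use Wilcoxon rank sum test in case of non-normal distribution". It does not assign any test to any hypothesis.

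On measurement, the Research Plan and Table 2 list hormone levels, metabolic factors, coagulation factors and anthropometric measurement as groups. Estrone, fat mass and an index of insulin sensitivity are not named in either place. Anthropometric data come from chart review.

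**The concern.** A hypothesis should have an analysis whose result could count for or against it. A between-arm test of insulin sensitivity asks whether route matters. It does not ask whether patients who gain more fat lose more insulin sensitivity, nor whether insulin sensitivity falls after treatment starts. Either of these is a fair reading of 2b, and neither has a planned test.

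For 2a, higher estrone and higher thrombogenic markers in the sublingual arms would fit the proposed mechanism, but would not show that the two go together. The Innovation section says that any group difference will be attributed to route of administration. That attribution does not establish that estrone is the reason.

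At stake is pilot information. The trial is meant to supply preliminary data for a larger trial, and estimates of these two associations would be useful output that the plan does not currently secure.

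**Working it through.** The documents give no alpha, power, effect size or SD for 2a or 2b, so there is no stated figure to reproduce. The check is first a matching of hypothesis to method.

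| Question | Analysis needed | Planned? |
|---|---|---|
| 2a: estrone by route | Between-arm test | Yes, if estrone is among the hormone levels |
| 2a: thrombogenic factors by route | Between-arm test | Yes |
| 2a: estrone linked to thrombogenic factors | Association | No |
| 2b read as association | Association | No |
| 2b read as before-after change | Within-patient change | No |

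Even the two rows marked yes need a decision. The design has three arms ("daily dose sublingual versus twice daily dose sublingual versus transdermal 17-beta estradiol in transgender female patients"), and the plan does not say which pairs are compared or whether the sublingual arms are pooled.

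**Why the arm test cannot stand in for the association.** Two simulations, 10,000 runs each, 23 patients per arm. Equal allocation, the correlation and the arm effects are assumptions; the plan states only block randomization.

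1. Correlation of -0.5 between fat mass and insulin sensitivity, no arm difference, three arms: an arm t-test rejects in 5.0% of runs, a correlation test in the pooled 69 patients in 99.5%.
2. Two arms differing by 1 SD on both variables, no association within arms: the arm t-tests reject in about 92% of runs for each variable, the arm-adjusted association in 5.3%.

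Both follow from how the cases were built. They show that the two kinds of test answer different questions. They do not estimate what this trial will find.

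**What an added association analysis could detect.** Inputs from the Subjects section: target 70, enrolment 80, dropout 15%, so 80 × 0.85 = 68 completers. Assumed: two-sided alpha 5%, power 80%, arms pooled, one observation per patient.

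- Smallest detectable |r| = tanh[(1.960 + 0.842) / √(N − 3)]
- N = 68: tanh(2.802 / 8.062) = 0.334
- N = 70: tanh(2.802 / 8.185) = 0.330
- Range: 0.35 at N = 60, 0.31 at N = 80
- Adjusting for arm (two indicators) and one baseline value uses three more degrees of freedom: at N = 68, tanh(2.802 / √62) = 0.34
- Within one arm of 23: 0.56

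Power = Φ[atanh(r)·√(N − 3) − 1.960]. At N = 70 it is 38%, 72% and 93% for |r| = 0.2, 0.3 and 0.4.

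**Effect of a noisy proxy.** If the adiposity proxy had reliability 0.5 (assumed), a true correlation of 0.30 would appear as 0.30 × √0.5 = 0.21. At N = 69 power falls from about 71% to about 42%. The smallest detectable true correlation at N = 68 rises to 0.334 / 0.707 = 0.47.

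**The case against.** Four points on the other side deserve weight.

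- **2a is mainly an arm contrast.** Its directional prediction concerns route, and the clause about estrone can be read as rationale. This stands: the plan does test the main prediction of 2a, and only the link is left out.
- **2b may be a before-after statement.** The sentences that follow it discuss fat gain under estradiol in general. That reading is reasonable, but no within-patient analysis is planned, so it does not close the gap. It does mean that the fix should cover both readings.
- **A regression would not prove the causal wording.** Estrone and adiposity are post-randomization variables, and the Dosing guidelines titrate to hormone levels, so estrone within an arm may track dose and response. Adjusting for arm also removes the between-route estrone difference that 2a is about. This stands in full, and the added results can only be exploratory.
- **It is a pilot, and this is secondary.** True, and it limits the severity.

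A reader might also infer that the trial will report a null arm comparison as its answer to 2b. The documents do not support that, because the statistical section ties the t-test to no hypothesis. What can be said is that 2b has no planned test. Nor does the 5% rejection rate in the first simulation measure harm to this trial, since the arm effect there was set to zero.

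**Conclusion.** The point holds. It rests on the text alone: 2b has no planned analysis under either reading, and the estrone link in 2a is untested, while the arm contrasts in 2a are covered. The detectable correlation of about 0.33 is an illustration under the stated assumptions, since the documents give no expected correlation.

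A reader might infer that the remedy costs nothing because the data are already collected. That is conditional. It is true only if estrone, an adiposity measure and an insulin-sensitivity marker fall within the listed categories, and none is named.

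This is a cheap improvement to the plan and not a threat to the trial's main result.

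**What to change.** In Statistical methods and Data Analysis:

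1. **Name the variables and time points.** State which estrone, adiposity and insulin-sensitivity measures come from the hormone, anthropometric and metabolic rows of Table 2. If one is not collected, reword the hypothesis to the proxy that is, or to an arm comparison.
2. **For 2b,** report within-patient change from baseline in the adiposity measure and in the insulin-sensitivity marker. Then regress change in the marker on change in adiposity, adjusted for arm and the baseline value. There is no untreated arm, so change from baseline cannot be separated from the passage of time.
3. **For 2a,** keep the arm comparisons as the main test. Add a regression of one named key thrombogenic factor on estrone, with and without adjustment for arm. Thrombin is a natural candidate, since the Limitations section singles it out if the full panel proves too costly.
4. **Label both regressions exploratory and associational.** If all visits are used, separate within-patient from between-patient effects, because a single random-effect slope blends them.

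The cost is a few lines of text if the measures already exist, and a few more tests to interpret with caution. If a measure has to be added, the documents do not allow its cost to be estimated. Rewording the hypothesis avoids it.
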